4.1.2 Missing Incomplete Dates for Prior or Concomitant Medications

Missing or partial medication start or stop dates will be imputed for the purpose of determining whether the medication is taken concomitantly. Data handling rules for missing or partial start/stop date medications are detailed in the table below. The missing or partial dates will be displayed in the data listings as reported on the eCRF rather than the imputed dates.

Imputation rules for missing or partial dates (D=day, M=month, Y=year, T=time)			
Parameter	Missing	Additional conditions	Imputation Rule
Start date	D only	M and Y same as M and Y of first dose of study drug	Date of first dose of study drug
		M and/or Y not same as M and Y of first dose of study drug	First day of month
	M and D	Y same as Y of first dose of study drug	Date of first dose of study drug
		Y not same as Y of first dose of study drug	Use Jan 01 of Y
	M, D and Y	None--date completely missing	Date of first dose of study drug
	Stop date	M and Y same as M and Y of end of study	Date of end of study
		M and/or Y not same as M and Y of end of study	Last day of month
		Y same as Y of end of study	Date of last dose of study drug
		Y not same as Y of end of study	Use Dec 31 of Y
	M, D and Y	Medications that are not marked as ongoing - date completely missing	Date of end of study

4.2. Sample Size

This is an exploratory trial to characterize safety, tolerability, and pharmacokinetics of single dose of RSM01 mAb administered by either IV or IM routes. The trial is designed to be descriptive and is not based on evaluation of a formal null hypotheses. Therefore, this study is not powered to detect any differences in potential safety observations between treatment groups. Data from approximately 56 participants will be available for analysis: 28 participants in the Dose Escalation Phase Cohorts and 28 participants in the Dose Expansion Phase Cohort.

Assuming that all cohorts are allowed to undergo treatment, approximately 48 participants will be exposed to RSM01, and approximately 8 participants will receive Placebo.

With N=6 participants (per RSM01 arm in Dose Escalation Phase cohorts), there is approximately 80% (90%) power to observe at least one AE if the true AE rate is 23.53% (31.87%). With N=24 participants (across all active doses of RSM01 in the Dose Escalation Phase cohorts or the Dose Expansion Phase Cohort), there is approximately 80% (90%) power to observe at least one AE if the true AE rate is 6.49% (9.15%). Across all active doses of RSM01 (N=48), there is approximately 80% (90%) power to observe at least one AE if the true AE rate is 3.3% (4.68%).

4.3. Randomization and Blinding

The first participant in each Dose Escalation Phase cohort will not be randomized and will receive RSM01 dose level appropriate to the assigned cohort in a single-blinded fashion: participants will be blinded to treatment, but site will not be blinded to treatment. Subsequent participants in the cohort will be double-blinded: participants and site personnel, except for the study pharmacist, will be blinded to treatment. The study pharmacist will know assignment to provide doses of RSM01 and Placebo to the clinic that are appropriately masked to the blinded treating nurse/physician.

The remaining 6 participants in each cohort (Cohorts 1, 2, 3 and 4) will be randomized 5:1 to receive either RSM01 or placebo. Cohorts 2 and 3 will be enrolled in parallel using 1:1 randomization. The overall ratio of RSM01 to placebo will be 6:1 in each cohort. The Expansion Phase cohort (Cohort 5) will be randomized 6:1 to receive either RSM01 IM (N=24) or placebo (N=4).

Randomization in each cohort will be based on a randomly generated sequence of participant identification (identifier) numbers (randomization schedule) using a validated Interactive Voice/Web Response System (IXRS).

The randomization schedule will be prepared by a statistician who will not be involved in the analysis of the study in order to maintain the blind of the study team.

With the exception of the first sentinel participant in each of the Dose Escalation Phase cohorts who will each receive the respective dose of RSM01, the study is double-blind: participants and all study personnel will be blinded to the randomization.

An interim analysis will be performed after availability of Cohort 2, Cohort 3, and Cohort 4 Day 30 data (see [Section 11](#)). Firewalled roles will be involved in the interim analysis to create unblinded datasets and perform analyses. The investigator will remain blinded. The sponsor will review blinded (pooled) safety data by cohort and unblinded aggregated PK data by treatment group (RSM01 vs. placebo) within and across cohorts. The sponsor will be blinded at the participant level throughout the study. For expedited safety reporting to regulatory authorities,

pharmacovigilance unblinding will be performed as required. Information regarding unblinding for the interim analysis is contained in a separate unblinding plan.

The IXRS will be programmed with blind-breaking instructions. In addition, instructions on emergency unblinding in case of system outage will be provided.

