### 6.5.2. Masking

The study is double-blind: participants and all study personnel will be blinded to the randomization, with one exception: the first sentinel participant in each Dose Escalation Phase cohort will be single-blinded (participant-blinded) and receive the respective dose of RSM01. Authorized study site personnel will administer doses.

The unblinded investigational pharmacist will provide the prepared doses of RSM01 and Placebo to the clinic appropriately masked to the blinded treating nurse/physician.

Only the following personnel will have access to the treatment allocation while the study remains blinded to other personnel:

- Pharmacist preparing the RSM01 and Placebo doses
- Biostatistician preparing the randomization list
- Biostatistician preparing the IDMC data, as applicable, and for the interim analysis
- Pharmacometrist preparing the PK data for IDMC (as applicable) and for the interim analysis
- IDMC members, as applicable
- Unblinded study Monitors.

Additionally, the supplies manager/designate and quality assurance personnel of the sponsor, as well as the IXRS system setup person and PK simulation and modeling vendor will have access to unblinding information.

All unblinded persons must take care to not reveal individual group assignments to any other member of the study team.

Any study staff that become inadvertently unblinded must not participate in the evaluation of AEs. A delegation of authority log will be maintained by the site and will identify the individual(s) authorized to function as individuals with access to study blinding information.

The interim analysis will be performed by an unblinded statistician. The investigator will be blinded during the entire study.

Blinding will be maintained during the aggregated PK data review to select the Dose Expansion Phase cohort dose and during interim analysis.

The sponsor will review aggregated safety data by cohort only (data from both RSM01 and Placebo participants will be included) and will review aggregated PK data by treatment group (RSM01 vs. Placebo) within and across cohorts for the following purposes: 1) selecting dosing for the Dose Expansion Phase cohort, and 2) reviewing the interim analysis to inform a decision and plan for the infant study. Although the sponsor will be blinded throughout the study, such review of aggregated data could potentially lead to individual unblinding. An unblinding plan will be prepared to include unblinding details.

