9.1 Adverse Events

9.1.1 Adverse Events Definitions and Reporting

An adverse event (AE) is defined as any untoward medical occurrence in a patient or clinical study participant, temporally associated with the use of study intervention, whether or not considered related to the study intervention.

A treatment-emergent AE (TEAE) is defined as any event not present before study intervention administration or any event already present that worsens in severity or frequency after study intervention administration.

A serious AE (SAE) is defined as any AE that results in any of the following outcomes: death, a life-threatening AE, inpatient hospitalization or prolongation of existing hospitalization, a persistent or significant incapacity or substantial disruption of the ability to conduct normal activities of daily living, or a congenital anomaly or birth defect. Important medical events that may not result in death, be life threatening, or require hospitalization may be considered serious when, based upon appropriate medical judgment, they may jeopardize the participant and may require medical or surgical intervention to prevent one of the outcomes listed in this definition.

An AE of special interest (AESI) is a preidentified and predefined event that has the potential to be causally associated with a study intervention that the sponsor will carefully monitor.

The AE's relationship to study treatment will be evaluated by the investigator or medically qualified designee (ie, investigator, study physician). The following relationships will be collected on eCRF: related, not related.

The severity of AEs will be classified by the investigator as mild, moderate, severe or potentially life threatening. An overall AE summary will be generated presenting the frequency and percentage of participants and the number of AEs for the following:

- Any TEAE
- Any treatment-related TEAE
- Any grade 1 TEAE
- Any grade 2 TEAE
- Any grade 3 or higher TEAE
- Any treatment-related grade 3 or higher TEAE
- Any SAE
- Any treatment-related SAE
- Any TEAE leading to dose interruption (IV route of administration)
- Any TEAE leading to study withdrawal
- Any death
- Any AESI

All AEs will be coded using MedDRA (version to be delineated in the CSR). The TEAEs will also be summarized by system organ class (SOC), preferred term (PT), by severity and relationship to study treatment.

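### The four sentinels, non-randomised and known to the site to be on RSM01, are pooled unmarked into the RSM01 safety columns, so assessor knowledge could influence the investigator-judged AE summaries on one side only

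*SAP*

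**What the plan says.** SAP 4.3 sets sentinels apart from everyone else: "The first participant in each Dose Escalation Phase cohort will not be randomized and will receive" RSM01 at the cohort's dose, and "participants will be blinded to treatment, but site will not be blinded to treatment". Protocol 6.5.2 agrees that the sentinel of each escalation "cohort will be single-blinded (participant-blinded) and receive the respective dose of RSM01". The other six participants in each escalation cohort "will be randomized 5:1 to receive either RSM01 or placebo", double-blind, and Cohort 5 is randomised 24 to 4.

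The analysis sections do not carry this distinction through. SAP 3 counts the sentinel in each RSM01 group of six. SAP 4.4 defines the safety population as everyone treated, grouped by what they received, and SAP 9 bases every safety summary on it. The display groups in SAP 4 are the five RSM01 regimens, Total RSM01 and three placebo groups, with none for sentinels.

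The judgements are made at the site. Protocol 8.2 gives causality, and intensity of unsolicited AEs, to the investigator or sub-investigator. Protocol 8.2.3.1 has investigators grade solicited AEs during confinement. SAP 9.1.1 tabulates "Any treatment-related TEAE", with similar lines for related grade 3 or higher events and related SAEs.

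Protocol 6.5.2 also says, without repeating the sentinel exception, "The investigator will be blinded during the entire study", and protocol 10.1.2 likewise describes the investigator as blinded until the primary endpoint analyses are done.

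**The concern.** Relatedness and intensity are the parts of the primary safety endpoint that depend most on judgement. An assessor who knows that a participant received active drug may call relatedness or grade an event differently from one who does not. Here that knowledge can exist by design only for RSM01 recipients: 4 of 48 on RSM01 against 0 of 8 on placebo.

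In a descriptive trial the tabulated percentages are the result, and placebo columns stand beside the RSM01 columns. In a group of six, one call made with knowledge of treatment can create or remove an apparent signal at a dose level. As planned, the summary tables do not let a reader see whether that has happened.

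The documents also leave open who evaluates a sentinel's AEs. One passage makes the site unblinded for that participant; others describe the investigator as blinded with no exception.

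**Working it through.** **Inputs.** One sentinel in each of Cohorts 1-4, always RSM01 (SAP 4.3). Six RSM01 and one placebo per escalation cohort, sentinel included (SAP 3). Cohort 5: 24 RSM01, 4 placebo (SAP 4.3). Totals: 48 RSM01, 8 placebo (SAP 4.2).

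**The plan's own figures.** SAP 4.2 gives AE rates at which the chance of at least one AE is 80% (90%). With P = 1 − (1 − p)^n:
- n = 6, p = 23.53% (31.87%): 80.0% (90.0%)
- n = 24, p = 6.49% (9.15%): 80.0% (90.0%)
- n = 48, p = 3.3% (4.68%): 80.0% (90.0%)

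All six reproduce. They count sentinels in n, and this point does not affect them.

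**Share of sentinels, w.**
- Each escalation RSM01 group: 1/6 = 16.7%
- All escalation RSM01: 4/24 = 16.7%
- IV RSM01: 3/18 = 16.7%; IM RSM01: 1/30 = 3.3%
- Total RSM01: 4/48 = 8.3%
- Placebo: 0/8

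**Effect of one changed call.** 1/6 = 16.7 points in a cohort; 1/24 = 4.2 points in escalation RSM01; 1/48 = 2.1 points in Total RSM01.

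**Expected shift.** Let d be the difference in the probability of a related AE that is due only to the assessor knowing the treatment. The shift in the reported percentage is w × d. The documents give no value for d, so the range below is an assumption. The sign could be either way.

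| Assumed d (points) | One escalation cohort | Total RSM01 |
|---|---|---|
| ±10 | ±1.7 | ±0.8 |
| ±20 | ±3.3 | ±1.7 |
| ±30 | ±5.0 | ±2.5 |
| ±50 | ±8.3 | ±4.2 |

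**For scale.** Exact 95% intervals are 0 to 36.9% for 0/8, 0.4 to 64.1% for 1/6 and 2.3 to 20.0% for 4/48.

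**Randomised participants only.** RSM01: 5 × 4 = 20 in escalation and 20 + 24 = 44 overall. Placebo: 4 and 8. The AE rate that gives an 80% (90%) chance of at least one event, 1 − (1 − P)^(1/n), becomes 7.7% (10.9%) for n = 20 and 3.6% (5.1%) for n = 44. The upper exact 95% limit for zero events goes from 7.4% (0/48) to 8.0% (0/44).

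**The case against.** Several stronger conclusions are tempting, and the documents do not support them.

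- *A reader might infer that the RSM01-placebo comparison is biased.* No such comparison is planned for AEs. Protocol 9.1 and SAP 4.2 call the trial descriptive, and the AE outputs are counts, percentages and exact intervals within groups. Bias is a possibility here, not something shown. The blinded assessor already knows that an escalation participant has a 5/6 = 83.3% chance of active drug; for a sentinel this becomes certainty, so the added knowledge is limited.
- *A reader might call the sentinels open-label.* They are blinded themselves, so their own reporting is protected. After confinement ends on Day 3 they record solicited events in the diary through Day 7 (protocol 8.1.9). Solicited local AEs are related by rule (SAP 9.1.3), and fever, redness and most laboratory grades rest on numeric cut-offs (protocol 10.4).
- *A reader might infer a breach of the protocol's own rule*, "Any study staff that become inadvertently unblinded must not participate in the evaluation of AEs". That rule covers accidental unblinding. The site's knowledge of sentinels is planned, and protocol 6.5.2 opens by naming the exception.
- *A reader might quote a shift of 4/48 = 8.3 points in Total RSM01.* That requires all four sentinels to have an AE called related solely because of the assessor's knowledge. It is the extreme case.

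It is also fair to say that dropping sentinels does not turn the totals into a single randomised comparison, since they pool sequential cohorts and two allocation ratios. The SAP already lists study drug administration and all AEs, so sentinel events may be traceable by a determined reader.

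What remains is that causality for AEs other than solicited local ones, unsolicited intensity, and solicited grading during confinement are exposed to assessor knowledge on the RSM01 side only. Nothing in the planned tables separates those records.

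**Conclusion.** The point holds as a risk that the planned tables cannot show or rule out, and as an inconsistency in the text on blinding. It does not show that any safety percentage is wrong.

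The possible effect is small in Total RSM01: 2.1 points for one changed call, and 0.8 to 4.2 points over the assumed range of d, against exact intervals that are much wider. It matters more within a six-person cohort, where one call is worth 16.7 points.

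The conclusion rests on two readings. First, the site staff who know the sentinel's treatment include those who judge the AEs; the documents neither state nor exclude this. Second, readers will set the RSM01 columns beside placebo even though no test is planned. A supplementary summary is justified because it is cheap and removes a source of assessor knowledge that exists in one arm only. The full safety population should stay as the main analysis.

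**What to change.** 1. Keep the full safety-population tables as the main analysis.
2. In SAP 9.1, add one supplementary set restricted to randomised double-blind participants: the overall AE summary, treatment-related TEAEs, and TEAEs and solicited AEs by severity. Present it for the Dose Escalation Phase (20 v 4) and overall (44 v 8). Per-cohort tables of 5 v 1 would add almost nothing.
3. Flag sentinels in all AE listings.
4. State that any descriptive remark setting RSM01 against placebo on relatedness or severity is based on the supplementary set.
5. Reconcile the unqualified statements of investigator blinding in protocol 6.5.2 and 10.1.2 with SAP 4.3, and state who assesses sentinel AEs. The documents do not settle this, so the sponsor must say which description is correct.

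The cost is a few repeated tables from data already collected, a listing flag and a text correction, best specified before unblinding. The supplementary set has 44 rather than 48 RSM01 participants, so its intervals are slightly wider.

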4.4. Analysis Populations

Population	Description
Enrolled population	All participants enrolled for screening. Participants randomly assigned to study treatment will be classified according to the intervention they were randomized to receive.
Safety Population	All participants who received the study treatment. Participants will be analyzed according to the intervention they received.
Per protocol (PP) Population	All participants who received study treatment and did not have a significant protocol deviation. Participants will be analyzed according to the intervention they received.
PK Population	All participants who received RSM01 who have a baseline and at least one post-baseline PK result. Participants will be analyzed according to the intervention they received.
Immunogenicity Population	All participants who received the study treatment and have at least one valid post-baseline ADA sample. Participants with no baseline ADA assessment are assumed to be negative at baseline. Participants will be analyzed according to the intervention they received.

5. Participant Disposition

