**Table 6: Populations for Analyses**

Population	Description
Intention to treat (ITT) PK population	All participants who received the study intervention. Participants will be analyzed according to the intervention actually received.
Per protocol (PP) PK population	All participants who received RSM01 and did not significantly deviate from study procedures, and who have at least one, non-zero PK result available. Participants will be analyzed according to the intervention actually received.
Safety	All participants who received the study intervention. Participants will be analyzed according to the intervention actually received.
Immunogenicity population	All participants who received the study intervention and have at least one valid ADA result. Participants will be analyzed according to the intervention actually received.

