### **9.3.4. Pharmacokinetics**

All available PK data will be summarized at the time of dose selection for the Dose Expansion Phase, and for the interim and primary analyses when all participants reach Day 91 and Day 151, respectively.

RSM01 capillary blood concentrations and the following PK parameters,  $AUC_{0-\infty}$ ,  $AUC_{0-t}$ ,  $C_{min}$ ,  $C_{max}$ , or  $C_0$ ,  $C_{D91}$ ,  $C_{D151}$ ,  $T_{max}$ ,  $t_{1/2}$ ,  $CL$  and  $Vz$ , will be summarized by treatment group. Each of the PK parameters will be summarized using descriptive statistics (e.g., arithmetic mean, standard deviation, arithmetic percent CV, median, minimum, maximum, geometric mean, and geometric percent CV), and the number of participants, as appropriate.

The proportion of participants with observed  $C_{D151}$  concentrations above the estimated EC90 for RSM01 (based on available pre-clinical data) will be summarized by treatment group. Exact 95% confidence interval will be calculated on the percentages.

PK will be summarized in the PP PK population.

In addition to calculating the PK parameters using noncompartmental analysis (NCA) methods, RSM01 capillary blood and venous serum-concentration data obtained in this study will be used to develop a population PK model that will aid in the prediction of dose or doses to be administered in infants and to assess potential covariates. The venous serum will be used for developing the model and not for the NCA analysis.

This analysis will be described in an independent analysis plan and reported separately.

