8.1. Pharmacokinetic Concentrations

Whole blood samples on VAMS and serum samples will be collected for measurement of RSM01 concentrations in capillary blood and venous serum as below:

Dose Escalation Phase:

- At Visit 1 (Day 1), PK blood draw will occur pre-dosing, within 5 minutes (\pm 1 minute) after end of infusion for IV dosing only, and at 8-hours (\pm 0.5 hours) post-dose for both IV and IM doses.
- Visit 2 (Day 2): 24-hours (\pm 1 hours)
- Visit 3 (Day 3): (\pm 0 day)
- Visit 4 (Day 6): (\pm 1 day)
- Visit 5 (Day 8): Days 8-10
- Visit 6 (Day 15): (\pm 3 days)
- Visit 7 (Day 29): Days 29-35
- Visit 8 (Day 61): (\pm 7 days)
- Visit 9 (Day 91): (\pm 7 days)
- Visit 10 (Day 121): (\pm 7 days)
- Visit 11 (Day 151): (\pm 7 days)
- Discontinuation visit

Dose Expansion Phase:

- At Visit 1 (Day 1): pre-dose

- Visit 2 (Day 8): Days 8-10
- Visit 3 (Day 29): Days 29-35
- Visit 4 (Day 91): (\pm 7 days)
- Visit 5 (Day 151): (\pm 7 days)
- Discontinuation visit

Individual capillary blood concentration of RSM01 and time deviation data for PK population will be presented in data listings. Capillary blood concentration data will be summarized by scheduled time point for the PP population using descriptive statistics (non-missing observations (N), arithmetic mean (Mean), standard deviation (SD), coefficient of variation (CV%), median, minimum, maximum, Q1 and Q3. Capillary blood concentration data will also be summarized by ADA status using the PK population.

Descriptive statistics of capillary blood concentration of RSM01 data will be calculated using values with the same precision as the source data and rounded for reporting purposes only. The following conventions will be applied when reporting descriptive statistics of PP PK concentration data:

- Mean, Min, Median, Max, Q1, Q3: 3 significant digits
- SD: 4 significant digits
- CV%: 1 decimal place

Concentrations of RSM01 that are below the lower limit of quantification (BLQ) before the first quantifiable concentration will be treated as zero for descriptive statistics. Below the limit of quantification values after the first quantifiable concentration will be set as missing and excluded for summary statistics.

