Mean (\pm SD) capillary blood concentrations of RSM01 versus scheduled time profiles will be plotted by treatment on both linear and semi-logarithmic scales for PK population. Individual capillary blood concentrations versus actual time profiles will be plotted on both linear and semi-logarithmic scales for the PP population. The ADA status for each subject will be displayed on the individual profiles and for ADA positive participants, the titer results will be plotted on the secondary Y-axis.

The same analyses will be performed for venous serum (exploratory objective).

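### The SAP's PK Population requires a baseline PK result, so an RSM01 recipient with no pre-dose result loses valid post-dose data in three PK displays and their serum counterparts

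*SAP*

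**What the plan says.** SAP 4.4 (Analysis Populations) defines the PK Population as "All participants who received RSM01 who have a baseline and at least one post-baseline PK result".

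Protocol Table 6 has two PK populations. The ITT PK population is "All participants who received the study intervention". The PP PK population is "All participants who received RSM01 and did not significantly deviate from study procedures, and who have at least one, non-zero PK result available". Neither asks for a baseline sample. Protocol 9.3.4 adds: "PK will be summarized in the PP PK population".

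SAP 8.1 assigns three capillary outputs to the PK Population:
- the listing: "Individual capillary blood concentration of RSM01 and time deviation data for PK population will be presented in data listings";
- the ADA subgroup table: "Capillary blood concentration data will also be summarized by ADA status using the PK population";
- the mean (SD) concentration plot, "versus scheduled time profiles will be plotted by treatment on both linear and semi-logarithmic scales for PK population".

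SAP 8.1 closes by repeating all of this for venous serum as an exploratory objective. The concentration summary by time point and the individual profiles (SAP 8.1) and the PK parameter listings and summaries (SAP 8.2) use the PP population, which has no baseline condition. SAP 8.3 names no population for dose proportionality or bioavailability.

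**The concern.** A pre-dose RSM01 concentration should carry almost no PK information here. The trial is first-in-human, exclusion 13 bars anyone already dosed in it, and exclusion 10 bars antibody or biologic therapy in the 180 days before Day 1. SAP 8.1 and 8.2 set values below quantification to zero when they precede the first quantifiable concentration, so a normal pre-dose result enters as zero.

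Making membership depend on that result means a participant with a full, valid set of post-dose samples can be left out of a display for want of a value everyone expects to be zero. The rule does not serve as an assay check either: it asks whether a pre-dose result exists, not what it is. A participant with an odd non-zero baseline stays in; one with a spoiled tube goes out.

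The same SAP table does the opposite for immunogenicity: a participant with no baseline ADA assessment is kept and taken as negative. Pre-dose PK and ADA samples share one collection window, about an hour before dosing. If that collection fails, the participant stays in the Immunogenicity Population but leaves the table relating concentration to ADA status.

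With six RSM01 recipients per escalation cohort, one omission is visible in a mean profile or a subgroup table.

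**Working it through.** **1. Inputs.** RSM01 recipients: 6 in each of Cohorts 1 to 4 and 24 in Cohort 5 (SAP 3), so 4 × 6 + 24 = 48. The documents give no loss rate for pre-dose samples; 2%, 5% and 10% are assumed to show a range.

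**2. The plan's own figures.** The plan states nothing numerical about the PK Population. Its only sizing statement is the probability of seeing at least one AE (SAP 4.2), which is 1 − (1 − p)^n. For n = 6, 1 − (1 − 0.2353)^6 = 80.0% and 1 − (1 − 0.3187)^6 = 90.0%, as stated; the n = 24 and n = 48 figures also reproduce. The same formula is used below.

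**3. Where an RSM01 recipient with no pre-dose result appears**

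| Output | Population | Included? |
|---|---|---|
| Concentration listing (8.1) | PK | No |
| Concentration by ADA status (8.1) | PK | No |
| Mean (SD) profile (8.1) | PK | No |
| Concentration summary by time point (8.1) | PP | Yes* |
| Individual profiles with ADA status (8.1) | PP | Yes* |
| PK parameters (8.2) | PP | Yes* |
| Dose proportionality, bioavailability (8.3) | not named | Undetermined |

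*Unless the missing sample is recorded as a significant deviation. SAP 5.2 has a significance flag but no definition.

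**4. Size of one exclusion.** Escalation arm: 1/6 = 16.7%. Cohort 5: 1/24 = 4.2%. As a gauge of precision, the 95% t half-width for a mean, t(0.975, n−1)/√n, goes from 1.05 SD at n = 6 to 1.24 SD at n = 5.

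**5. Chance of at least one exclusion in an arm of 6, if one particular matrix must be present:** 1 − (1 − q)^6.
- q = 2%: 1 − 0.98^6 = 11.4%
- q = 5%: 1 − 0.95^6 = 26.5%
- q = 10%: 1 − 0.90^6 = 46.9%

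**6. The same, if either serum or capillary blood counts.** Assuming independent losses, both must fail, so q is replaced by q².
- q = 2%: 1 − 0.9996^6 = 0.2%
- q = 5%: 1 − 0.9975^6 = 1.5%
- q = 10%: 1 − 0.99^6 = 5.9%

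Losses from one failed visit would not be independent, so the true figure under this reading lies between steps 5 and 6. SAP 4.4 does not say which reading applies.

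**The case against.** The strongest reply is that little of consequence depends on this clause. The outputs closest to the PK endpoint are on the PP population, as protocol 9.3.4 intends, and the population PK model for infant dosing has its own plan. The individual profiles, with ADA status and titers overlaid, would still show the participant. All of that stands and keeps the point small.

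Protocol 9.3 also leaves it to the SAP to describe the analysis populations further, so a difference from Table 6 is not a fault in itself. That stands too. The case rests on the condition discarding valid data for no analytical gain, not on the difference alone. That the pre-dose value is uninformative is an inference from the design; no section says so, and assay background is not described.

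There are safeguards against loss. Participants are confined from Day -1 and sampled on site, and both matrices are drawn pre-dose. The SAP's baseline definition accepts repeat and unscheduled samples, and protocol 8.6 and 8.9 allow leftover neutralization and ADA samples to be used for drug concentration. These lower the probability but do not remove it; a redraw helps only if the failure is noticed before dosing.

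A reader might infer that some exclusion is close to certain, since 1 − (1 − q)^48 gives 62%, 91% or 99% over all 48 recipients. Those figures use assumed rates, require one particular matrix, and give half their weight to Cohort 5, where one loss is only 4%. If either matrix counts and losses are independent, they fall to about 2%, 11% and 38%. The arm-level figures are the ones to set beside the 17%.

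A reader might also blame this clause for the mismatch between PK-based and PP-based displays. The SAP splits its outputs between those populations anyway: an RSM01 recipient with a significant deviation can be in the PK Population but not in the PP population, whatever the baseline rule.

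**Conclusion.** The concern holds in a limited form. SAP 4.4 adds a baseline requirement found in neither protocol PK population. Followed as written, it removes a participant's valid post-dose concentrations from the capillary listing, the mean (SD) profile and the ADA-status summary, and from the parallel serum outputs. The condition has no evident benefit and runs against the SAP's own handling of a missing baseline ADA.

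The documents do not support reading this as damage to the noncompartmental PK parameters: those are reported on the PP population. Nor do they show harm to dose proportionality or bioavailability, for which no population is named.

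The size per event is certain: 6 to 5, or 24 to 23. The likelihood is not. It rests on assumed loss rates and on how an unstated matrix rule is read. In a descriptive trial this is a worthwhile tidy-up rather than a threat to the conclusions.

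**What to change.** In SAP 4.4, delete the baseline condition so that the PK Population is every RSM01 recipient with at least one post-dose PK result. State that this is applied separately to capillary blood and to serum. Footnote any missing pre-dose value in the affected displays.

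This should not be described as matching protocol Table 6: the ITT PK population takes all treated participants, placebo included, and the PP PK population has a deviation criterion and asks for a non-zero result. Nor should a missing pre-dose value be set to zero for the noncompartmental analysis. SAP 8.2 leaves missing concentrations missing, and the parameters are not governed by this population.

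The cost is a few words, a footnote, and one PK Population count per matrix in the disposition table (SAP 5.1). It is best done before unblinding. No analysis method changes.
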